# 12.4 Technical complaints and technical complaint samples

### 12.4.1 Reporting of technical complaints

All technical complaints on any of the following products:

- Insulin degludec/liraglutide 100 units/mL + 3.6 mg/mL(IDegLira), 3 mL pre-filled pen.
- Insulin degludec 100 Units/mL (IDeg), 3 mL pre-filled pen
- Liraglutide 6 mg/mL (Victoza®), 3 mL pre-filled pen
- Novo Nordisk needles for pre-filled pens,

Protocol Trial ID: NN9068-4148 UTN: U1111-1154-6671	CONFIDENTIAL	Date: Version: Status: Page:	07 October 2014 2.0 Final 51 of 84	
---	--------------	---------------------------------------	---	--

which occur from the time of first usage of the product until the time of the last usage of the product, must be collected and reported to Customer Complaint Center, Novo Nordisk.

Contact details (fax, e-mail and address) are provided in Attachment I to the protocol.

The investigator must assess whether the technical complaint is related to any AEs, SAEs, and/or MESI.

Technical complaints must be reported on a separate technical complaint form for each product listed. If the technical complaint involves more than one batch or lot number or more than one DUN, a technical complaint form for each batch or lot number or for each DUN must be completed.

The investigator must complete the technical complaint form in the eCRF within the following timelines of the trial site obtaining knowledge of the technical complaint:

Technical complaint assessed as related to an SAE within 24 hours

All other technical complaints within 5 calendar days

If the eCRF is unavailable or when reporting a technical complaint that is not subject related, the information must be provided on a paper form by fax, e-mail or courier to Customer Complaint Center, Novo Nordisk, within the same timelines as stated above.

# 12.4.2 Collection, storage and shipment of technical complaint samples

The investigator must collect the technical complaint sample and notify the monitor **within 5 calendar days** of obtaining the sample at trial site. The monitor must coordinate the shipment to Customer Complaint Center, Novo Nordisk (the address is provided in Attachment I) and ensure that the sample is sent as soon as possible. A print of the technical complaint form must be sent with the sample.

The investigator must ensure that the technical complaint sample contains the batch or lot number and, if available, the DUN.

If the technical complaint sample is unobtainable, the investigator must specify on the technical complaint form why it is unobtainable.

Storage of the technical complaint sample must be done in accordance with the conditions prescribed for the product. The shipment of the technical complaint sample should be done in accordance with the same conditions as for storage (see section 9.3).

Page:

52 of 84

# 12.5 Pregnancies in female subjects

Female subjects must be instructed to notify the investigator immediately if they become pregnant during the trial. The investigator must report any pregnancy in subjects who have received trial products.

The investigator must follow the pregnancy until the pregnancy outcome and the newborn infant is one month of age.

The investigator must report information about the pregnancy, pregnancy outcome, and health of the newborn infant(s), as well as AEs in connection with the pregnancy, and AEs in the foetus and newborn infant.

The following must be collected and reported by the investigator to Novo Nordisk - electronically (e.g. in PDF format), or by fax or courier:

### 1. Reporting of pregnancy information

Information about the pregnancy and pregnancy outcome/health of the newborn infant(s) has to be reported on Maternal Form 1A and 1B, respectively.

When the pregnancy outcome is abnormal (i.e. congenital anomalies, foetal death including spontaneous abortion and/or any anomalies of the foetus observed at gross examination or during autopsy), and/or when a congenital anomaly is diagnosed within the first month, further information has to be reported for the female subject on Maternal Form 2. In addition, information from the male partner has to be reported on the Paternal Form, after an informed consent has been obtained from the male partner.

Initial reporting and follow-up information must be reported within 14 calendar days of the investigator's first knowledge of initial or follow-up information.

### 2. Reporting of AE information

The investigator has to report AEs in connection with the pregnancy as well as in the foetus and newborn infant(s). The SAEs that must be reported include abnormal outcome, such as foetal death (including spontaneous abortion), and congenital anomalies (including those observed at gross examination or during autopsy of the foetus), as well as other pregnancy complications fulfilling the criteria of an SAE.

Forms and timelines for reporting AEs related to pregnancy:

Non-serious AEs:

• Paper AE form\* within 14 calendar days of the investigator's first knowledge of the initial or follow-up information to the non-serious AE

Protocol		Date:	07 October 2014	Novo Nordisk
Trial ID: NN9068-4148	CONFIDENTIAL	Version:	2.0	
UTN: U1111-1154-6671	CONFIDENTIAL	Status:	Final	
		Page:	53 of 84	

### SAEs:

- Paper AE form\* within 24 hours of the investigator's first knowledge of the SAE
- Paper safety information form **within 5 calendar days** of the investigator's first knowledge of the SAE
- **SAE follow-up information** to the AE form and/or safety information form **within 24 hours** of the investigator's first knowledge of the follow-up information
- \* It must be clearly stated in the AE diagnosis field on the AE form if the event occurred in the subject, foetus or newborn infant.

Any queries or follow-up requests from Novo Nordisk to non-serious AEs, SAEs and pregnancy forms must be responded to by the investigator **within 14 calendar days** from the date of receipt of the request, unless otherwise specified in the follow-up request.

### 12.6 Precautions and/or overdose

During treatment with insulin there is a risk of hypoglycaemia. Symptoms of hypoglycaemia usually occur suddenly and may include cold sweat, nervousness or tremor, anxious feelings, unusual tiredness, confusion, difficulty in concentrating, excessive hunger, temporary vision changes, headache, nausea and palpitation. Severe hypoglycaemia may lead to unconsciousness.

Hypoglycaemic episodes should be treated according to best practise at the discretion of the investigator. Attention should be given to the fact that the action profile of the insulin component in IDegLira and IDeg is long-acting and the prolonged effect may delay recovery from a hypoglycaemic episode.

Asymptomatic hypoglycaemia and symptoms of minor hypoglycaemia should be treated by ingestion of carbohydrate (for example juice). Severe hypoglycaemia resulting in loss of consciousness should be treated with parenteral glucose, glucagon or dextrose at the investigator's discretion.

From clinical trials and marketed use of Liraglutide overdoses up to 40 times the recommended maintenance dose (72 mg) have been reported. Events reported included severe nausea and severe vomiting. None of the reports included severe hypoglycaemia. All patients recovered without complications.

When initiating treatment with IDegLira or Liraglutide, the subject may in some cases experience loss of fluids/dehydration, due to vomiting, nausea or diarrhoea. It is important to avoid dehydration by drinking plenty of fluids.

For further information on IDeglira, IDeg or liraglutide, please see Investigator's Brochure, any updates hereof, and/or SmPCs/ local labelling, as applicable.

| Protocol | | Date: 07 October 2014 | Novo Nordisk | Version: 2.0 | Status: Final | Page: 54 of 84 |

# 12.7 Committees related to safety

# 12.7.1 Novo Nordisk safety committee

Novo Nordisk will constitute an internal IDegLira/NN9068 safety committee to perform ongoing safety surveillance. The safety committee will be informed about the results of on-going safety surveillance activities for the individual mono components IDeg and liraglutide, respectively.

# 12.7.2 Calcitonin monitoring committee

An independent committee of thyroid experts is established to perform calcitonin monitoring of all calcitonin values  $\geq$ 20 ng/L in subjects throughout the trial (except for screening failures). The committee will provide recommendations to investigators with regards to further investigation and treatment of the individual subject. The committee will be blinded to trial treatment.

For further instructions on calcitonin monitoring, see appendix D.

# 12.7.3 Event adjudication committee

An external event adjudication committee is established to perform qualitative or quantitative validation of selected AEs according to pre-defined diagnostic criteria. The validation is based on review of pre-defined clinical source data related to the specific AE. The events are reviewed by the event adjudication committee in an independent and blinded manner.

The following AEs will be adjudicated in this trial:

- Death
- Acute coronary syndrome (myocardial infarction or hospitalisation for unstable angina)
- Cerebrovascular event (transient ischemic attack or stroke)
- Heart failure requiring hospital admission
- Coronary revascularisation
- Pancreatitis or clinical suspicion of pancreatitis
- Neoplasm
- Thyroid disorders requiring thyroidectomy

AEs for adjudication must be reported according to section 12.2. In addition the specific event adjudication document collection form has to be completed and relevant pre-defined documents provided within 14 calendar days of the investigator's first knowledge of the AE, according to instructions in the event adjudication site manual. The investigator should provide the medical documentation within 4 weeks of event identification.

Event adjudication will not be performed for AEs in screening failures. For further information regarding definitions, rationales, and events that will be adjudicated, see appendix B.

| Protocol | | Date: 07 October 2014 | Novo Nordisk | UTN: U1111-1154-6671 | CONFIDENTIAL | CONFIDENTIAL | CONFIDENTIAL | Page: 55 of 84 | CONFIDENTIAL | CONFIDENTIAL | CONFIDENTIAL | Page: 55 of 84 | CONFIDENTIAL | CONFIDENTIAL | CONFIDENTIAL | Page: 55 of 84 | CONFIDENTIAL | CONFIDENTIAL | CONFIDENTIAL | CONFIDENTIAL | CONFIDENTIAL | CONFIDENTIAL | CONFIDENTIAL | CONFIDENTIAL | CONFIDENTIAL | CONFIDENTIAL | CONFIDENTIAL | CONFIDENTIAL | CONFIDENTIAL | CONFIDENTIAL | CONFIDENTIAL | CONFIDENTIAL | CONFIDENTIAL | CONFIDENTIAL | CONFIDENTIAL | CONFIDENTIAL | CONFIDENTIAL | CONFIDENTIAL | CONFIDENTIAL | CONFIDENTIAL | CONFIDENTIAL | CONFIDENTIAL | CONFIDENTIAL | CONFIDENTIAL | CONFIDENTIAL | CONFIDENTIAL | CONFIDENTIAL | CONFIDENTIAL | CONFIDENTIAL | CONFIDENTIAL | CONFIDENTIAL | CONFIDENTIAL | CONFIDENTIAL | CONFIDENTIAL | CONFIDENTIAL | CONFIDENTIAL | CONFIDENTIAL | CONFIDENTIAL | CONFIDENTIAL | CONFIDENTIAL | CONFIDENTIAL | CONFIDENTIAL | CONFIDENTIAL | CONFIDENTIAL | CONFIDENTIAL | CONFIDENTIAL | CONFIDENTIAL | CONFIDENTIAL | CONFIDENTIAL | CONFIDENTIAL | CONFIDENTIAL | CONFIDENTIAL | CONFIDENTIAL | CONFIDENTIAL | CONFIDENTIAL | CONFIDENTIAL | CONFIDENTIAL | CONFIDENTIAL | CONFIDENTIAL | CONFIDENTIAL | CONFIDENTIAL | CONFIDENTIAL | CONFIDENTIAL | CONFIDENTIAL | CONFIDENTIAL | CONFIDENTIAL | CONFIDENTIAL | CONFIDENTIAL | CONFIDENTIAL | CONFIDENTIAL | CONFIDENTIAL | CONFIDENTIAL | CONFIDENTIAL | CONFIDENTIAL | CONFIDENTIAL | CONFIDENTIAL | CONFIDENTIAL | CONFIDENTIAL | CONFIDENTIAL | CONFIDENTIAL | CONFIDENTIAL | CONFIDENTIAL | CONFIDENTIAL | CONFIDENTIAL | CONFIDENTIAL | CONFIDENTIAL | CONFIDENTIAL | CONFIDENTIAL | CONFIDENTIAL | CONFIDENTIAL | CONFIDENTIAL | CONFIDENTIAL | CONFIDENTIAL | CONFIDENTIAL | CONFIDENTIAL | CONFIDENTIAL | CONFIDENTIAL | CONFIDENTIAL | CONFIDENTIAL | CONFIDENTIAL | CONFIDENTIAL | CONFIDENTIAL | CONFIDENTIAL | CONFIDENTIAL | CONFIDENTIAL | CONFIDENTIAL | CONFIDENTIAL | CONFIDENTIAL | CONFIDENTIAL | CONFIDENTIAL | CONFIDENTIAL | CONFIDENTIAL | CONFIDENTIAL | CONFIDENTIAL | CONFIDENTIAL

# 13 Case report forms

Novo Nordisk will provide a system for the eCRF. This system and support services to the system will be supplied by a vendor.

When entering data into the eCRF, trial site staff must ensure that all relevant questions are answered, and that no empty data field exists. If a test or an assessment has not been done and will not be available, or if the question is irrelevant (e.g. is not applicable), indicate this according to the data entry guidelines.

The following will be provided as paper CRFs only:

• Pregnancy forms

In addition paper AE forms, safety information forms and technical complaint forms will be provided. These must be used when access to the eCRF is revoked.

On the paper CRF forms print legibly, using a ballpoint pen. Ensure that all questions are answered, and that no empty data blocks exist. Ensure that no information is recorded outside the data blocks. If a test/assessment has not been done and will not be available, indicate this by writing "ND" (not done) in the appropriate answer field in the CRF. If the question is irrelevant (e.g. is not applicable) indicate this by writing "NA" (not applicable) in the appropriate answer field. Further guidance can be obtained from the instructions in the CRF.

The investigator must ensure that all information is consistent with the source documentation. By electronically signing the case book in the eCRF, the investigator confirms that the information in the eCRF and related forms is complete and correct.

### 13.1 Corrections to case report forms

Corrections to the eCRF data may be made by the investigator or the investigator's authorised staff. An audit trail will be maintained in the eCRF application containing as a minimum: the old and the new data, identification of the person entering the data, date and time of the entry and reason for the correction.

If corrections are made by the investigator's authorised staff after the date the investigator has signed the case book, the case book must be signed and dated again by the investigator.

Corrections to the data on paper CRFs may only be made by drawing a straight line through the incorrect data and then writing the correct entry next to the data that was crossed out. Each correction must be initialled, dated and explained (if necessary). If corrections are made by the investigator's authorised staff after the date of the investigator's signature on the affirmation statement, the affirmation statement must be signed and dated again by the investigator.

Protocol Trial ID: NN9068-4148 UTN: U1111-1154-6671	CONFIDENTIAL	Date: Version: Status: Page:	07 October 2014   Novo Nor 2.0 Final 56 of 84	disk
---	--------------	---------------------------------------	--	------

Corrections necessary after the CRFs have been removed from the trial site must be documented on a data clarification form or a monitor-initiated discrepancy form. If the affirmation statement for the subject has not yet been signed, any corrections must be approved by the investigator or her/his authorised staff. If the affirmation statement for the subject has already been signed, the investigator must approve any correction.

# 13.2 Case report form flow

The investigator must ensure that data is recorded in the eCRF as soon as possible, preferably within 5 days after a site visit/telephone contact. The SMPG values and corresponding insulin doses for titration purpose must preferably be entered within 24 hours after the site visit/telephone contact on week days throughout the trial.

Once data has been entered, it will be available to Novo Nordisk for data verification and validation purposes. Queries will be generated in the eCRF, and the investigator should solve these queries on an ongoing basis throughout the trial.

Site specific eCRF data (in an electronic readable format) will be provided to the trial site before access to the eCRF is revoked. This data must be retained at the trial site.

| Protocol | Date: 07 October 2014 | Novo Nordisk | Version: 2.0 | Status: Final |

Page:

57 of 84

# 14 Monitoring procedures

During the course of the trial, the monitor will visit the trial site to ensure that the protocol is adhered to, that all issues have been recorded, to perform source data verification and to monitor drug accountability. The first monitoring visit will be performed no later than 6 weeks after FPFV. The monitoring visit intervals will depend on the outcome of the remote monitoring of the eCRF, the trial site's recruitment rate and the compliance of the trial site to the protocol and ICH GCP, but will not exceed 8 weeks.

# 14.1 Source data verification and source data requirements

The monitor must be given direct access to source documents (original documents, data and records). Direct access includes permission to examine, analyse, verify and reproduce any record(s) and report(s) that are important to the evaluation of the trial. If the electronic medical record does not have a visible audit trail, the investigator must provide the monitor with signed and dated printouts. In addition the relevant trial site staff should be available for discussions at monitoring visits and between monitoring visits (e.g. by telephone).

Monitors must review the subject's medical records and other source data (e.g. the diaries) to ensure consistency and/or identify omissions compared to the CRF. If discrepancies are found, the investigator and/or relevant trial site staff should be available for discussion at/between monitoring visits.

All data must be verifiable in source documentation other than the CRF. This must be defined in a source document agreement at each trial site. There must only be one source defined at any time for any data element.

The monitor will collect CRF pages and other trial related forms containing data from screening failures. Source data verification requirements for screening failures are described in section 8.1.3.

Source data generated by the trial site can be corrected by another person than the person entering the source data if accepted by local regulations; any correction must be explained, signed and dated by the person making the correction.

For SMPG values it is accepted that the earliest practically retainable record should be considered source data. Therefore, the data recorded by the BG-meter and transcribed into the diary by the subject will be considered source data. The diary will be considered the source document with respect to:

- Date and fasting SMPG values
- Date, time and dose of trial product
- Date and time for hypoglycaemic episodes

Page: 58 of 84	Protocol Trial ID: NN9068-4148 UTN: U1111-1154-6671	CONFIDENTIAL	Date: Version: Status:	07 October 2014 2.0 Final	Novo Nordisk
----------------	---	--------------	------------------------------	---------------------------------	--------------

The original diaries must not be removed from the trial site, unless they form part of the CRF and a copy is kept at the site.

A follow-up letter (paper or electronic) will be sent to the investigator following each monitoring visit addressing any action to be taken.

# 15 Data management

Data management is the responsibility of Novo Nordisk.

Appropriate measures, including encryption of data files containing person identifiable data, will be used to ensure confidentiality of subject data, when they are transmitted over open networks.

Data from central laboratories will be transferred electronically to Novo Nordisk from the laboratory performing the analyses. Data from special laboratories may be transferred to Novo Nordisk via the central laboratory. In cases where data is transferred via non-secure electronic networks, data will be encrypted during transfer. Laboratory reports will be provided directly to the investigator for storage at trial site.

The subject and any biological material obtained from the subject will be identified by subject number and trial identification number. Appropriate measures such as encryption or leaving out certain identifiers will be enforced to protect the identity of subjects in all presentations and publications as required by local, regional and national requirements.

# 16 Computerised systems

Novo Nordisk will capture and process clinical data using computerised systems that are described in Novo Nordisk Standard Operating Procedures and IT architecture documentation. The use and control of these systems are documented.

Investigators working on the trial may use their own electronic systems to capture source data.

| Protocol | | Date: 07 October 2014 | Version: 2.0 | Status: Final | Page: 59 of 84 |

# 17 Statistical considerations

Novo Nordisk will analyse and report data from all sites together.

All analyses of efficacy and safety endpoints will be based on the full analysis set (FAS). The analysis of the primary endpoint will be repeated on the per-protocol (PP) analysis set and the completer analysis set (CAS) for sensitivity purposes. All efficacy endpoints will be summarised using the FAS and safety endpoints will be summarised using the safety analysis set (SAS).

The impact of protocol deviations and outliers may be investigated further in sensitivity analyses if deemed relevant.

Unless otherwise specified, all continuous measurements will be summarised descriptively at each visit by treatment using observed data. After 26 weeks of treatment, descriptive statistics will be presented based both on observed and last observation carried forward (LOCF) imputed data. Endpoints that are analysed untransformed and endpoints that are not formally analysed are summarised by the arithmetic mean, standard deviation (SD), median, and minimum and maximum value. Endpoints that are analysed log-transformed are supplemented with the geometric mean and coefficient of variation (CV).

For measurements over time, mean values will be plotted to explore the trajectory over time. LOCF imputed data will be used as the basis for plotting data, if not otherwise specified. For endpoints that are analysed log-transformed, the geometric mean values will be plotted.

A standard analysis of covariance (ANCOVA) model will be applied for the continuous primary and secondary endpoints. The model includes treatment and previous OAD treatment (metformin or metformin in combination with one of the following: AGI, SU, glinides and TZD as fixed effects and the corresponding baseline value as covariate. In the following, this model will be referred to as the standard ANCOVA model.

Presentation of results from a statistical analysis will include the estimated mean treatment effects (Least Square Means [LSMeans]) for absolute values and change from baseline. In addition, estimated mean treatment difference (or ratio) will be presented together with the two-sided 95% confidence interval and corresponding two-sided 5% p-value.

### Handling of missing data

The expected percentage of missing data is around 15%. In accordance with industry guidance endpoints will be assessed at frequent visits and also on subjects who withdraw prematurely. This will facilitate an analysis in accordance with ITT principles. Also, the combined information on frequent outcomes and information on reason for drop-out is assumed to account for the missing data anticipated.

Protocol Trial ID: NN9068-4148 UTN: U1111-1154-6671	CONFIDENTIAL	Date: Version: Status: Page:	07 October 2014 2.0 Final 60 of 84	Novo Nordisk
---	--------------	---------------------------------------	---	--------------

If an assessment has been made both at screening (Visit 1) and randomisation (Visit 2), and if not otherwise specified, the value from the randomisation visit will be used as the baseline value. If the value measured at the randomisation visit is missing and the assessment also has been made at screening, then the screening value will be used as the baseline value.

Missing values (including intermittent missing values) will be imputed using the LOCF method. Subjects without data after randomisation will be included by carrying forward their baseline value. LOCF has been a standard approach in diabetes trials for many years, and was used as the primary analysis in both IDegLira and IDeg phase 3a trials. LOCF is considered to be an appropriate method in the context of TTT trials, where subjects after withdrawal typically continue their therapy using commercially available insulin. In previous TTT trials with IDegLira and IDeg, LOCF has generally provided similar results to alternative methods applied to handle missing data, such as repeated measures models and completer analyses. In this trial, similar sensitivity analyses will be made to examine the robustness of the LOCF method. The LOCF approach will also be used to impute missing values in CAS.

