Follow-up visit (FU)	SC	R	V	V	T	V	T	V	T	V	T	V	T	V	T	V	FU
Visit number															23		
							7		11		15		19		24 25		
							8		12		16		20		26		
	1	2	3	4	5	6	9	10	13	14	17	18	21	22	27	28	29
Time of visit (week)															21		
	-21		,	_	2		5 6		9	10	13	1.0	17	20	22	26	27
	-2	0	1	2	3	4	7	8	10 11	12	14 15	16	18 19	20	23 24	26	27
							_ ′		11		13		17		25		
Visit window (days)			±3	±3	±3	±3	±3	±3	±3	±3	±3	±3	±3	±3	±3	±3	+3
Hypoglycaemic episodes		X	X	X	X	X	X	X	X	X	X	X	X	X	X	X	X
ECG 	X															X	
Eye examination 5	X															X	
Physical examination	X															X	
Vital signs	X	X								X						X	
Antibodies		X								X						X	X
Biochemistry	X	X								X						X	
Haematology	X	X								X						X	
Hormones, calcitonin	X	X								X						X	
Lipids		X								X						X	
Urine dipstick		X								X						X	
Pregnancy test (blood sample)	X															X	
REMINDERS						•	•	•			•		•	•			
Handout ID card	X																
Handout and instruct in BG-meter use	X																
Attend visit fasting		X				X		Х		X		X		X		X	x 
IV/WRS call	X	X				X		X		X		X		X		X	Λ
Dispense trial product. Instruct																	<del>                                     </del>
and hand out Directions for Use.		X				X		X		X		X		X			
Drug accountability		X				X		X		X		X		X		X	
Handout and instruct in/collect diary	X	X	X	X		X		X		X		X		X		X	X
Collect first date and dose of trial			X														
Product  Collect last date and dose of trial		 	 	 	 				 							v	
product																X	
Confirmation of unchanged dose of metformin			X	X	X	X	X	X	X	X	X	X	X	X	X	X	
For liraglutide arm:																	
Confirmation of unchanged dose						X	X	X	X	X	X	X	X	X	X	X	
of liraglutide 																	
End of trial and sign off on case																	X
book	1	1	1	1	1	l	l	l	1	1	L		L	L			Щ

- 1. Screening must take place within 14 calendar days prior to randomisation.
- 2. For source data to be recorded in subject's diary prior to every PK sampling visit, please see section 8.3.4.
- 3. For IDeglira and IDeg arm: Daily pre-breakfast SMPG, last dose prior to titration and dose to be taken after titration must be recorded. For liraglutide arm: Pre-breakfast SMPG on 3 consecutive days prior to each visit/telephone contact must be recorded.

Protocol		Date:	07 October 2014	Novo Nordisk
Trial ID: NN9068-4148	CONFIDENTIAL	Version:	2.0	
UTN: U1111-1154-6671	CONFIDENTIAL	Status:	Final	
		Page:	14 of 84	

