### 8.2.8 Vital signs (blood pressure and pulse)

Diastolic blood pressure, systolic blood pressure and pulse (beats per minute) should be assessed while the subject is in a sitting position. Measurements should be performed after 5 minutes of rest.

Blood pressure must be measured three times at a visit and all three values should be recorded. The mean value will be calculated by the eCRF and must be in accordance with the relevant exclusion criterion, see section 6.3.

If the investigator suspects white coat hypertension at the screening visit and/or randomisation visit, one re-assessment of the systolic and diastolic blood pressure (as described above) is allowed.

| Protocol | | Date: 07 October 2014 | Novo Nordisk | UTN: U1111-1154-6671 | CONFIDENTIAL | CONFIDENTIAL | CONFIDENTIAL | Page: 32 of 84 | CONFIDENTIAL | CONFIDENTIAL | CONFIDENTIAL | Page: 32 of 84 | CONFIDENTIAL |

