#### **Pulse**

Change from baseline in pulse after 26 weeks of treatment will be analysed using the standard ANCOVA model.

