### Systolic and diastolic blood pressure

Change from baseline in systolic and diastolic blood pressure after 26 weeks of treatment will be analysed using the standard ANCOVA model.

| Protocol | Trial ID: NN9068-4148 | CONFIDENTIAL | CONFIDENTIAL | CONFIDENTIAL | CONFIDENTIAL | CONFIDENTIAL | CONFIDENTIAL | CONFIDENTIAL | CONFIDENTIAL | CONFIDENTIAL | CONFIDENTIAL | CONFIDENTIAL | CONFIDENTIAL | CONFIDENTIAL | CONFIDENTIAL | CONFIDENTIAL | CONFIDENTIAL | CONFIDENTIAL | CONFIDENTIAL | CONFIDENTIAL | CONFIDENTIAL | CONFIDENTIAL | CONFIDENTIAL | CONFIDENTIAL | CONFIDENTIAL | CONFIDENTIAL | CONFIDENTIAL | CONFIDENTIAL | CONFIDENTIAL | CONFIDENTIAL | CONFIDENTIAL | CONFIDENTIAL | CONFIDENTIAL | CONFIDENTIAL | CONFIDENTIAL | CONFIDENTIAL | CONFIDENTIAL | CONFIDENTIAL | CONFIDENTIAL | CONFIDENTIAL | CONFIDENTIAL | CONFIDENTIAL | CONFIDENTIAL | CONFIDENTIAL | CONFIDENTIAL | CONFIDENTIAL | CONFIDENTIAL | CONFIDENTIAL | CONFIDENTIAL | CONFIDENTIAL | CONFIDENTIAL | CONFIDENTIAL | CONFIDENTIAL | CONFIDENTIAL | CONFIDENTIAL | CONFIDENTIAL | CONFIDENTIAL | CONFIDENTIAL | CONFIDENTIAL | CONFIDENTIAL | CONFIDENTIAL | CONFIDENTIAL | CONFIDENTIAL | CONFIDENTIAL | CONFIDENTIAL | CONFIDENTIAL | CONFIDENTIAL | CONFIDENTIAL | CONFIDENTIAL | CONFIDENTIAL | CONFIDENTIAL | CONFIDENTIAL | CONFIDENTIAL | CONFIDENTIAL | CONFIDENTIAL | CONFIDENTIAL | CONFIDENTIAL | CONFIDENTIAL | CONFIDENTIAL | CONFIDENTIAL | CONFIDENTIAL | CONFIDENTIAL | CONFIDENTIAL | CONFIDENTIAL | CONFIDENTIAL | CONFIDENTIAL | CONFIDENTIAL | CONFIDENTIAL | CONFIDENTIAL | CONFIDENTIAL | CONFIDENTIAL | CONFIDENTIAL | CONFIDENTIAL | CONFIDENTIAL | CONFIDENTIAL | CONFIDENTIAL | CONFIDENTIAL | CONFIDENTIAL | CONFIDENTIAL | CONFIDENTIAL | CONFIDENTIAL | CONFIDENTIAL | CONFIDENTIAL | CONFIDENTIAL | CONFIDENTIAL | CONFIDENTIAL | CONFIDENTIAL | CONFIDENTIAL | CONFIDENTIAL | CONFIDENTIAL | CONFIDENTIAL | CONFIDENTIAL | CONFIDENTIAL | CONFIDENTIAL | CONFIDENTIAL | CONFIDENTIAL | CONFIDENTIAL | CONFIDENTIAL | CONFIDENTIAL | CONFIDENTIAL | CONFIDENTIAL | CONFIDENTIAL | CONFIDENTIAL | CONFIDENTIAL | CONFIDENTIAL | CONFIDENTIAL | CONFIDENTIAL | CONFIDENTIAL | CONFIDENTIAL | CONFIDENTIAL | CONFIDENTIAL | CONFIDENTIAL | CONFIDENTIAL | CONFIDENTIAL | CONFIDENTIAL |

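### Pulse and blood pressure are measured at two pre-treatment visits, but the ANCOVA adjusts only for the second; adding the Visit 1 value as a further covariate could gain some precision at almost no cost

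*Protocol*

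**What the plan says.** The flow chart (Protocol, Section 2) schedules vital signs at screening, randomisation, week 12 and week 26; the row opens "Vital signs X X". Section 8.2.8 also presumes blood pressure readings at both early visits, since it allows, "at the screening visit and/or randomisation visit, one re-assessment of the systolic and diastolic blood pressure". On replication within a visit it says "Blood pressure must be measured three times at a visit and all three values should be recorded", and the mean is used. It states no replication for pulse.

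The baseline rule is in Section 17, under the handling of missing data. Where an assessment was made at both visits, "the value from the randomisation visit will be used as the baseline value", unless otherwise specified. Only if the Visit 2 value is missing, "then the screening value will be used as the baseline value". The standard ANCOVA in Section 17 has treatment and previous oral antidiabetic treatment as factors and "the corresponding baseline value as covariate".

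Section 17.4.2.2 applies that model without exception: "Change from baseline in pulse after 26 weeks of treatment will be analysed using the standard" ANCOVA, and "Change from baseline in systolic and diastolic blood pressure after 26 weeks of treatment will be analysed using the standard" ANCOVA. The amendment texts that reproduce changes to Section 17 do not alter the baseline rule or these two analyses.

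**The concern.** For every subject with both readings, the Visit 1 value is collected and then left out of the model. Pulse and blood pressure vary from one visit to the next, so a single visit is a noisy measure of a subject's usual level. Averaging three blood pressure readings within a visit does not remove variation between visits. For pulse not even within-visit averaging is stated.

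Both readings precede randomised treatment, so adjusting for both cannot bias the randomised comparison. Screening is at most 14 days before randomisation, and subjects stay on their current oral treatment until Visit 2 (Section 8.1.2), so the Visit 1 reading may well carry information about week 26 beyond what Visit 2 supplies.

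What is at stake is the width of the confidence intervals for the treatment differences in pulse and blood pressure. These are listed safety endpoints in a trial meant to compare the combination with its components. No confirmatory conclusion depends on them.

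**Working it through.** **The plan's own figures.** The protocol gives no power or precision for pulse or blood pressure. Its only power figures are for HbA1c (Section 17.1), and they reproduce with one-sided 2.5% t-tests and SD 1.0:

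- Non-inferiority, 306 against 153 subjects, margin 0.4, true difference 0: 98.08% (stated 98.1%).
- Superiority, 360 against 180, difference 0.3: 90.67% (stated 90.7%).
- Product: 0.890 (stated 89.0%).

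The point below does not touch them.

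**Inputs.** From the protocol: readings at Visits 1, 2 and 28 (week 26), and 2:1:1 allocation of 720, so 360 against 180 in each comparison. Assumed, because the protocol gives none: equal variances at each visit (set to 1), r1 and r2 for the correlations of Visits 1 and 2 with week 26, and rb for the correlation between Visits 1 and 2.

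**Formulas for residual variance.**

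- Visit 2 only, as planned: 1 − r2².
- Visits 1 and 2 as separate covariates: 1 − (r1² + r2² − 2·r1·r2·rb)/(1 − rb²). With r1 = r2 = rb = r this is 1 − 2r²/(1 + r).

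With Visit 2 in the model, the treatment estimate is the same whether the response is the week 26 value or the change from Visit 2.

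**All correlations equal.**

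| r | Visit 2 only | Both visits | Variance ratio | Interval width ratio |
|---|---|---|---|---|
| 0.4 | 0.840 | 0.771 | 0.918 | 0.958 |
| 0.6 | 0.640 | 0.550 | 0.859 | 0.927 |
| 0.7 | 0.510 | 0.424 | 0.830 | 0.911 |

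So variance falls by about 8%, 14% and 17%, and intervals narrow by about 4%, 7% and 9%. At r = 0.6 the 95% half-width with 360 against 180 goes from 1.96·√(1/360 + 1/180)·√0.640 = 0.143 SD to 1.96·√(1/360 + 1/180)·√0.550 = 0.133 SD. A simulation of 4,000 trials at r = 0.6 gave standard errors of 0.0735 and 0.0678 (variance ratio 0.852). Mean estimates were 0.0016 and 0.0019 SD against a true value of 0, which is within simulation error.

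**Less favourable correlations.**

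- r1 = r2 = 0.55, rb = 0.7: 1 − 2·0.3025/1.7 = 0.644 against 0.698, a cut of about 8%.
- r2 = 0.5, r1 = 0.4, rb = 0.8: 1 − (0.16 + 0.25 − 0.32)/0.36 = 0.750 against 0.750. The gain is nil.

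**Why not simply use the two-visit mean.** If the response stays change from Visit 2 and the only covariate is the mean of Visits 1 and 2, the residual variance under equal correlations is 2(1 − r) − (1 − r)²/(2(1 + r)):

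- r = 0.4: 1.071 against 0.840, 28% higher.
- r = 0.6: 0.750 against 0.640, 17% higher.
- r = 0.7: 0.574 against 0.510, 12% higher.

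The Visit 2 noise is then in the response but no longer fully adjusted for. Using the mean consistently, in both the change and the covariate, avoids this, but it can still lose slightly when Visit 1 is the weaker predictor. In the nil-gain case above it gives 1 − 0.45²/0.9 = 0.775 against 0.750, about 3% worse.

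**The case against.** The strongest reply is that nothing here is wrong. The last value before randomised treatment, with screening as fallback, is a standard baseline, stated once and applied uniformly. The rule admits exceptions, so an analysis plan that is not shown could add one. Pulse and blood pressure are supportive, outside the test hierarchy, with no margin or power target. All of that stands, and it limits the point to an optional improvement.

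The second reply is that Visit 1 may be the poorer predictor. The flow chart marks Visits 2, 14 and 28 as fasting but not Visit 1, and Section 8.1.1 has metformin withheld on the day of a fasting visit until sampling and weighing are done. Visit 2 therefore resembles the week 26 conditions more closely. Visit 1 blood pressure is also an eligibility reading, although Section 8.2.8 treats the two early visits alike on re-assessment. This stands as a reason why the gain may be small or nil. It is no reason against a second covariate, which lets the data weight each visit.

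Three stronger readings are tempting, and the documents do not support them:

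- That the Visit 2 baseline biases the comparison. It does not; it is a pre-treatment value in a randomised comparison.
- That an 8% to 17% saving is established. It rests on assumed correlations, with Visit 1 taken to be as predictive as Visit 2.
- That the Visit 1 value is never used. It is the fallback when Visit 2 is missing.

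**Conclusion.** The point holds as a modest, optional gain in efficiency for pulse, systolic and diastolic blood pressure. Under assumed equal correlations of 0.4 to 0.7, adjusting for both pre-treatment values lowers residual variance by about 8% to 17% and narrows intervals by about 4% to 9%. The gain falls to nil in plausible cases where Visit 1 predicts week 26 less well. With Visit 1 as a separate covariate the residual variance cannot rise, so the downside is one degree of freedom in a model fitted to 720 randomised subjects. The primary HbA1c analysis, the test hierarchy and the sample size are unaffected.

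**What to change.** Add a sentence to the pulse and blood pressure paragraphs of Section 17.4.2.2, or to the analysis plan: for pulse, systolic and diastolic blood pressure, the standard ANCOVA also includes the Visit 1 value as a second covariate; baseline and change from baseline remain defined by Visit 2. Add a simple rule for missing values: if one of the two readings is missing, the other is used in its place. This agrees with the existing fallback and uses only pre-treatment data.

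Because baseline stays at Visit 2, carrying the baseline value forward for subjects without later data works as now. Do not substitute the two-visit mean as the only covariate while the response is change from Visit 2. The change needs no new measurement and affects no other endpoint.
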